5.2. Exclusion Criteria

Participants will be excluded from the study if any of the following criteria apply:

1. Clinically significant disease (including newly diagnosed malignancy or cardiovascular disease) or intention to have surgery during the study; or any other medical condition that, in the investigator's opinion, would confound the results of the study or put the participant at undue risk
2. Pregnant or intention to become pregnant during the study
3. Any severe systemic pSS manifestation that may put the participant at undue risk based on the investigator's opinion

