8.2.2. ESSDAI

The ESSDAI was designed to measure disease activity in patients with pSS.⁵ The ESSDAI consists of 12 domains, 11 related to organ involvement (cutaneous, pulmonary, renal, articular, muscular, peripheral nervous system, central nervous system, hematological, glandular, constitutional, and lymphadenopathic) and 1 biological domain reflecting B-cell activity (Section 10.7.1). The activity levels of each domain (range: 0-3 points) are multiplied by their respective weights (range: 1-6 points) to obtain the total score.

ESSDAI-related laboratory tests include the following:

- Gammaglobulins
- Cryoglobulins
- C3, C4 and CH50

The gammaglobulin and cryoglobulin results will be blinded postbaseline.

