10.7. Appendix 7: Efficacy Endpoint Data

10.7.1. ESSDAI

Table 7: ESSDAI: Domain and Item Definitions and Weights

Domain [Weight]	Activity level	Description
Constitutional [3] Exclusion of fever of infectious origin and voluntary weight loss	No = 0	Absence of the following symptoms
	Low = 1	Mild or intermittent fever (37.5 to 38.5°C)/night sweats and/or involuntary weight loss of 5 to 10% of body weight
	Moderate = 2	Severe fever (> 38.5°C)/night sweats and/or involuntary weight loss of > 10% of body weight
Lymphadenopathy [4] Exclusion of infection	No = 0	Absence of the following features
	Low = 1	Lymphadenopathy \geq 1 cm in any nodal region or \geq 2 cm in inguinal region
	Moderate = 2	Lymphadenopathy \geq 2 cm in any nodal region or \geq 3 cm in inguinal region, and/or splenomegaly (clinically palpable or assessed by imaging)
	High = 3	Current malignant B-cell proliferative disorder
Glandular [2] Exclusion of stone or infection	No = 0	Absence of glandular swelling
	Low = 1	Small glandular swelling with enlarged parotid (\leq 3 cm), or limited submandibular or lachrymal swelling
	Moderate = 2	Major glandular swelling with enlarged parotid (> 3 cm), or important submandibular or lachrymal swelling
Articular [2] Exclusion of osteoarthritis	No = 0	Absence of currently active articular involvement
	Low = 1	Arthralgias in hands, wrists, ankles, and feet, accompanied by morning stiffness (> 30 minutes)
	Moderate = 2	1 to 5 (of 28 total count) synovitis
	High = 3	\geq 6 (of 28 total count) synovitis
Cutaneous [3] Rate as “No activity” stable long-lasting features related to damage	No = 0	Absence of currently active cutaneous involvement
	Low = 1	Erythema multiforme
	Moderate = 2	Limited cutaneous vasculitis, including urticarial vasculitis, or purpura limited to feet and ankle, or subacute cutaneous lupus
	High = 3	Diffuse cutaneous vasculitis, including urticarial vasculitis, or diffuse purpura, or ulcers related to vasculitis

Table 7: ESSDAI: Domain and Item Definitions and Weights (Continued)

Domain [Weight]	Activity level	Description
Pulmonary [5] Rate as “No activity” stable long-lasting features related to damage, or respiratory involvement not related to the disease (tobacco use etc)	No = 0	Absence of currently active pulmonary involvement

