	Low = 1	Persistent cough or bronchial involvement with no radiographic abnormalities on radiography; or radiological or HRCT evidence of interstitial lung disease with: no breathlessness and normal lung function test
	Moderate = 2	Moderately active pulmonary involvement, such as interstitial lung disease shown by HRCT with shortness of breath on exercise (NHYA II) or abnormal lung function tests restricted to: 70% > DLCO ≥ 40% or 80% > FVC ≥ 60%
	High = 3	Highly active pulmonary involvement, such as interstitial lung disease shown by HRCT with shortness of breath at rest (NHYA III, IV) or with abnormal lung function tests: 70% > DLCO ≥ 40% or 80% > FVC ≥ 60%
Renal [5] Rate as “No activity” stable long-lasting features related to damage, and renal involvement not related to the disease. If biopsy has been performed, please rate activity based on histological features first	No = 0	Absence of currently active renal involvement with proteinuria < 0.5 g/day, no hematuria, no leucocyturia, no acidosis, or long-lasting stable proteinuria due to damage
	Low = 1	Evidence of mild active renal involvement, limited to tubular acidosis without renal failure or glomerular involvement with proteinuria (between 0.5 and 1 g/day) and without hematuria or renal failure (GFR ≥ 60 mL/min)
	Moderate = 2	Moderately active renal involvement, such as tubular acidosis with renal failure (GFR < 60 mL/min) or glomerular involvement with proteinuria between 1 and 1.5 g/day and without hematuria or renal failure (GFR ≥ 60 mL/min) or histological evidence of extra-membranous glomerulonephritis or important interstitial lymphoid infiltrate
	High = 3	Highly active renal involvement, such as glomerular involvement with proteinuria > 1.5 g/day or hematuria or renal failure (GFR < 60 mL/min), or histological evidence of proliferative glomerulonephritis or cryoglobulinemia related renal involvement
Muscular [6] Exclusion of weakness due to corticosteroids	No = 0	Absence of currently active muscular involvement
	Low = 1	Mild active myositis shown by abnormal EMG or biopsy with no weakness and creatine kinase (N < CK ≤ 2N)

Table 7: ESSDAI: Domain and Item Definitions and Weights (Continued)

Domain [Weight]	Activity level	Description
	Moderate = 2	Moderately active myositis proven by abnormal EMG or biopsy with weakness (maximal deficit of 4/5), or elevated creatine kinase ($2N < CK \leq 4N$)

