	High = 3	Highly active myositis shown by abnormal EMG or biopsy with weakness (deficit $\leq 3/5$) or elevated creatine kinase ($> 4N$)
PNS [5] Rate as “No activity” stable long-lasting features related to damage or PNS involvement not related to the disease	No = 0	Absence of currently active PNS involvement
	Low = 1	Mild active peripheral nervous system involvement, such as pure sensory axonal polyneuropathy shown by NCS or trigeminal (V) neuralgia
	Moderate = 2	Moderately active PNS involvement shown by NCS, such as axonal sensory-motor neuropathy with maximal motor deficit of 4/5, pure sensory neuropathy with presence of cryoglobulinemic vasculitis, ganglionopathy with symptoms restricted to mild/moderate ataxia, CIDP with mild functional impairment (maximal motor deficit of 4/5 or mild ataxia), or cranial nerve involvement of peripheral origin (except trigeminal [V] neuralgia)
	High = 3	Highly active PNS involvement shown by NCS, such as axonal sensory-motor neuropathy with motor deficit $\leq 3/5$, peripheral nerve involvement due to vasculitis (mononeuritis multiplex, etc), severe ataxia due to ganglionopathy, CIDP with severe functional impairment: motor deficit $\leq 3/5$ or severe ataxia
CNS [5] Rate as “No activity” stable long-lasting features related to damage or CNS involvement not related to the disease	No = 0	Absence of currently active CNS involvement
	Low = 1	Moderately active CNS features, such as cranial nerve involvement of central origin, optic neuritis, or multiple sclerosis–like syndrome with symptoms restricted to pure sensory impairment or proven cognitive impairment
	High = 3	Highly active CNS features, such as cerebral vasculitis with cerebrovascular accident or transient ischemic attack, seizures, transverse myelitis, lymphocytic meningitis, multiple sclerosis–like syndrome with motor deficit

Table 7: ESSDAI: Domain and Item Definitions and Weights (Continued)

Domain [Weight]	Activity level	Description
Hematological [2] For anemia, neutropenia, and thrombopenia, only autoimmune cytopenia must be considered Exclusion of vitamin or iron deficiency, drug-induced cytopenia	No = 0	Absence of autoimmune cytopenia

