The activity levels of each domain (range: 0-3 points or 2 points) are multiplied by their respective weights (range: 1-7 points) to obtain the total score. The final score, the sum of all domain scores, falls between 0 (no disease activity) and 135. For CNS, score values indicates (0= None, 2=Moderate and 3= High). If a domain score is missing, final score will not be calculated.

These 11 components are present in database and these components gradings are multiplied by their weights as mentioned in table above at database level. The values for each domain are obtained from CRF and then the Total Score consisting of 11 components is available at database level and hence, no score derivation is required.

Responder with low disease activity (clinESSDAI score of < 5 points) is obtained at week 24 and 48⁴.

2) Patient-reported symptoms: This will be measured with ESSPRI.

ESSPRI is a questionnaire that has been developed to measure self-reported symptoms in participants with pSS.

The ESSPRI has 3 items that measure dryness, fatigue, and pain over a recall period of “the last 2 weeks.” Each item includes a numeric rating scale ranging from 0 “No symptoms (dryness, fatigue or pain)” to 10 “Maximal imaginable (dryness, fatigue or pain).” These individual 3 item scores are obtained from electronic clinical outcome assessment (eCOA).

The ESSPRI Total score is derived by summation of all the three numeric scores and then averaging the same. If any of the three numeric scores are missing, the total score will be missing.

The ESSPRI total score ranges from 0 to 10, with higher scores indicating more symptoms.

Higher score in ESSPRI reflects more severe symptomatology.

[figure not shown]
Clinically meaningful response is defined as a decrease of ≥ 1 point or $\geq 15\%$ from baseline.

3) Tear gland function: This will be measured with Schirmer’s test and OSS.

The Schirmer’s test measures total tear secretion is used to identify aqueous-deficient dry eye, the type of dry eye primarily associated with Sjögren’s syndrome. In the absence of anesthesia, the Schirmer test measures reflex tearing, while the test performed with anesthesia measures basal tear secretion.

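### Protocol Table 7 gives the same lung-function range to pulmonary levels 2 and 3 (12 or 18 clinESSDAI points), and its code for moderate CNS activity (1) disagrees with the SAP's (2)

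*Protocol*

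**What the plan says.** Protocol Section 8.2.2 describes the ESSDAI as 11 organ domains "and 1 biological domain reflecting B-cell activity (Section 10.7.1"), and so sends the reader to Table 7 for the level definitions. Section 8.2.3 gives the clinESSDAI weights (Table 5) but no separate level definitions. Table 7 is therefore the only full set of definitions in these documents.

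**Pulmonary, Table 7.**
- Moderate = 2: interstitial lung disease with breathlessness on exercise ("NHYA II) or abnormal lung function tests restricted to: 70% > DLCO ≥ 40% or 80% > FVC ≥ 60" percent).
- High = 3: interstitial lung disease with breathlessness "at rest (NHYA III, IV) or with abnormal lung function tests: 70% > DLCO ≥ 40% or 80% > FVC ≥ 60" percent.

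**CNS.**
- Table 7 lists levels 0, 1 and 3. The row labelled Low = 1 begins "Moderately active CNS features, such as cranial nerve involvement of central origin, optic neuritis".
- SAP Section 13.1.1 states: "For CNS, score values indicates (0= None, 2=Moderate and 3= High").

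SAP Section 13.1.1 takes the domain values from the CRF and the total from the database, with no re-derivation at analysis.

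**The concern.** In both pulmonary rows the lung-function range is joined to the breathlessness criterion by an 'or', so lung function alone can qualify a participant for either level. Table 7 gives no tie-break.

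For CNS, both documents have a single category between none and high. They disagree about the number attached to that category, not about which category a rater would choose. Within Table 7, the four other rows worded as moderately active (pulmonary, renal, muscular and PNS) are all level 2; the PNS row, for example, begins "Moderately active PNS involvement shown by NCS".

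The level entered at the site is the level analysed. A clinESSDAI change of 3 or more points sets responder status and the QW/Q2W switch, triggers reversion to QW, earns 3 STAR points and defines an improvement endpoint. ESSDAI has its own improvement endpoint at 3 points. A scoring ambiguity larger than 3 points can therefore affect both secondary results and dosing decisions.

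**Working it through.** **Inputs.** Weights from Protocol Table 5 (the clinESSDAI weights match SAP Table E): pulmonary 5 on ESSDAI and 6 on clinESSDAI; CNS 5 on both. Domain score = level × weight, and the total is the sum over domains.

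**Reproducing the stated totals** (maximum level × weight, in Table 5 order):
- ESSDAI: 6+12+4+6+9+15+15+18+15+15+6+2 = 123, as stated.
- clinESSDAI: 8+12+4+9+9+18+18+21+15+15+6 = 135, as stated.

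The weights and ranges are sound; the fault lies in the level definitions.

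**Size of each ambiguity.**

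| Finding | clinESSDAI | ESSDAI |
|---|---|---|
| Pulmonary, level 2 or 3 | 2×6 = 12 or 3×6 = 18 (gap 6) | 2×5 = 10 or 3×5 = 15 (gap 5) |
| CNS moderate, code 1 or 2 | 1×5 = 5 or 2×5 = 10 (gap 5) | 5 or 10 (gap 5) |

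A participant with interstitial lung disease and DLCO 50%, or FVC 70%, meets the lung-function limits of both rows. DLCO below 40% or FVC below 60% lies outside the printed range in both.

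**Pulmonary: effect on change.** If the same finding is rated 2 at one visit and 3 at another, the change is ±6 on clinESSDAI and ±5 on ESSDAI. The problem also arises when the shared range is read the same way at every visit:

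| Clinical course | Range read as Moderate | Range read as High |
|---|---|---|
| Breathlessness at rest improves to exercise only, DLCO still in range | (2−3)×6 = −6 | (3−3)×6 = 0 |
| Lung function normalises, exercise breathlessness persists | (2−2)×6 = 0 | (2−3)×6 = −6 |

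With other domains unchanged, each course is a response of at least 3 points under one reading only. On ESSDAI the changes are −5 and 0, then 0 and −5.

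**CNS: effect on change, one code used throughout.**

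| CNS move | Code 1 | Code 2 |
|---|---|---|
| Moderate to none | −5 | −10 |
| High to moderate | −10 | −5 |
| None to moderate | +5 | +10 |
| Moderate to high | +10 | +5 |
| None to high | +15 | +15 |

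Let x be the net change in the other domains.
- Response (total ≤ −3), CNS improving: a change of −5 needs x ≤ 2 and −10 needs x ≤ 7, so the codes disagree for x = 3 to 7.
- Response, CNS worsening: +5 needs x ≤ −8 and +10 needs x ≤ −13, so they disagree for x = −12 to −8.
- Increase (total ≥ +3), CNS worsening: they disagree for x = −7 to −3.
- Increase, CNS improving: they disagree for x = 8 to 12.

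The CNS code thus changes a 3-point outcome only when other domains move in the opposite direction. A spurious change in a CNS category that has not moved needs both codes to be in use.

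**What is unaffected.** Every disputed domain score is at least 5. The endpoints below 5, CRESS item 1 and the mild/moderate reclassification come out the same under either reading.

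**STAR.** With o points from the other four domains (maximum 3+1+1+1 = 6), the systemic item decides response when o < 5 and o + 3 ≥ 5, that is, o = 2, 3 or 4.

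**Scale, assuming 30 observed participants.** One flip is 1/30 = 3.3 percentage points. One spurious 6-point change moves the clinESSDAI mean by 6/30 = 0.2; a 5-point change moves a mean by 5/30 = 0.17.

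**The case against.** The strongest objection is that exposure may be close to nil. The schedule of activities contains no lung-function test. Table 7 rates as no activity "stable long-lasting features related to damage, or respiratory involvement not related to the disease", and exclusion criterion 3 removes "Any severe systemic pSS manifestation that may put the participant at undue risk" in the investigator's opinion. No document shows a participant at a disputed level. All of this stands, and it limits the expected effect.

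The pulmonary rows also differ in lead term and breathlessness class, and both give examples rather than exhaustive criteria. Raters therefore have other guidance, the Investigator Site File holds further instructions, and the same physician is preferred at all visits. That lowers the chance of inconsistent rating. It does not remove the overlap when lung function decides the level, and the two courses tabulated above need no inconsistency between visits.

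On CNS, the SAP codes a category called moderate and does not list its features. But each document has only one category between none and high, so the numbers do conflict.

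Responder status and reversion also have a severity-reclassification route, which can give the same decision under both codes. If CNS goes from moderate to none while other domains rise from 0 to 3, the total falls from 5 or 10 to 3, a response either way. The CNS ranges above are therefore necessary conditions for a different dosing decision, not sufficient ones. They apply directly to the 3-point endpoints and the STAR item.

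Finally, the primary endpoint is safety and nothing is tested formally. That argues against a higher rating, but clinESSDAI also steers dosing frequency.

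**Conclusion.** The concern holds: the level definitions are wrong as written and should be fixed. The pulmonary overlap is the more consequential part. It is worth 6 clinESSDAI or 5 ESSDAI points and can by itself create or remove a 3-point change. The CNS disagreement is worth 5 points on either index and matters for a 3-point outcome only with an opposing change of 3 to 7 or 8 to 12 points in other domains, or if both codes are in use.

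Confidence in the discrepancy is high. Its practical effect is unknown and probably small, because the number of participants with pulmonary or CNS activity at these levels is not given. The eCRF, site file and parent-study coding are not available, so mis-scoring is possible but not shown. The clinESSDAI baseline is a parent-study value (SAP Table C), which makes that coding relevant, though nothing indicates that it differed. These documents alone cannot settle which cut-off or code is correct.

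**What to change.** 1. Reconcile the Table 7 pulmonary Moderate and High rows, the Table 7 CNS row and SAP Section 13.1.1 with the instrument publications cited in Protocol Sections 8.2.2 and 8.2.3, so that each finding maps to one level and both documents use one CNS code.
2. Confirm that the eCRF and the parent-study coding match the reconciled definitions, and notify sites.
3. Before database lock, query every recorded pulmonary level 2 or 3 and any CNS level 1, including baselines carried over from the parent study.
4. As an editorial item, check and correct the source citation under Table 7. It points to reference 8, whose title concerns ESSPRI, whereas references 5 and 6 are the ones cited for ESSDAI and clinESSDAI.

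The cost is a text correction to the protocol appendix and the SAP, a note to sites and a targeted data query. No new assessments are needed.

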10.8. Appendix 8: ACR-EULAR Classification Criteria

The ACR-EULAR classification of pSS applies to any individual who meets the following inclusion and exclusion criteria and has a score of ≥ 4 when summing the weights from the items presented in Table 8.

Inclusion Criteria

Inclusion criteria apply to any patient with ≥ 1 symptom of ocular or oral dryness, defined as a positive response to ≥ 1 of the following questions:

1. Have you had daily, persistent, troublesome dry eyes for more than 3 months?
2. Do you have a recurrent sensation of sand or gravel in the eyes?
3. Do you use tear substitutes more than 3 times a day?
4. Have you had a daily feeling of dry mouth for more than 3 months?
5. Do you frequently drink liquids to aid in swallowing dry food?

OR suspicion of pSS from the ESSDAI questionnaire (with ≥ 1 positive domain item)

Exclusion Criteria

Prior diagnosis of any of the following conditions would exclude diagnosis of pSS and participation in pSS studies or therapeutic studies because of overlapping clinical features or interference with criteria tests:

- AIDS
- Active hepatitis C infection (with positive PCR)
- Sarcoidosis
- Amyloidosis
- Graft-versus-host disease
- History of head and neck radiation treatment
- IgG4-related disease

Table 8: ACR-EULAR Classification Criteria for Primary Sjögren’s Syndrome

Item	Weight/Score
Labial salivary gland with focal lymphocytic sialadenitis and focus score of $\geq 1^a$	3
Anti-Ro/SS-A positive	3
OSS of $\geq 5^{18}$ (or van Bijsterveld score of $\geq 4^{19}$) on at least 1 eye	1
Schirmer’s test of ≤ 5 mm/5 minutes on at least 1 eye ^b	1
UWSF rate of ≤ 0.1 mL/min ^{20,b}	1

Source: Shiboski et al²¹

ACR = American College of Rheumatology; EULAR = European Alliance of Associations for Rheumatology; OSS = ocular staining score; SS-A = Sjögren’s syndrome-related antigen A; UWSF = unstimulated whole salivary flow

- ^a A pathologist with expertise in the diagnosis of focal lymphocytic sialadenitis and focus score count (based on number of foci per 4 mm²) should perform the histopathologic examination following a protocol by Daniels et al²².
- ^b Patients who are normally taking anticholinergic drugs should be evaluated for objective signs of salivary hypofunction and ocular dryness after a sufficient interval off these medications so that these components can be a valid measure of oral and ocular dryness.

ICF	informed consent form
ICH	International Council for Harmonisation of Technical Requirements for Pharmaceuticals for Human Use
█	█
IgG	immunoglobulin G
█	█
IMP	investigational medicinal product
IRR	Infusion-related reaction
IV	intravenous
LLN	Lower Limit Normal
MCS	Mental component summary
MedDRA	Medical Dictionary for Regulatory Activities
█	█
NCI	National Cancer Institute
OLE	open-label extension
OSS	ocular staining score
█	█
PCR	polymerase chain reaction
PCS	Physical component summary
PD	pharmacodynamic(s)
PDMP	Protocol Deviations Management Plan
█	█
PI	Principal Investigator
PK	pharmacokinetic(s)
PKAS	pharmacokinetic analysis set
pSS	primary Sjögren’s syndrome
PT	preferred term
PYFU	patient years of follow-up

Copyright © 2009, 2010, 2012, 2016, 2018, 2019, 2021, 2024 IQVIA. All rights reserved. The contents of this document are confidential and proprietary to IQVIA Holdings Inc. and its subsidiaries. Unauthorized use, disclosure or reproduction is strictly prohibited.

QW	once weekly
Q2W	every 2 weeks
RF	rheumatoid factor
RNA	Ribonucleic acid
SAE	serious adverse event
SAF	Safety analysis set
SAP	statistical analysis plan
SBP	systolic blood pressure
SD	standard deviation
█	█
SFV	safety follow-up visit
SGUS	salivary gland ultrasonography
SoA	schedule of activities
SOC	system organ class
SS-A	Sjögren’s syndrome–related antigen A
SS-B	Sjögren’s syndrome–related antigen B
STAR	Sjögren’s Tool for Assessing Response
█	█
TEAE	treatment-emergent adverse event
ULN	Upper Limit Normal
UWSF	unstimulated whole salivary flow
█	█
WHO DRUG	World Health Organization Drug Dictionary
WOCBP	women of childbearing potential

DEFINITIONS OF TERMS

Term	Definition
Non-responder	Participant who does not have a reduction in ClinESSDAI score of ≥ 3 points and/or a change in score that alters their disease severity category
Responder	Participant who has a reduction in ClinESSDAI score of ≥ 3 points and/or a change in score

Copyright © 2009, 2010, 2012, 2016, 2018, 2019, 2021, 2024 IQVIA. All rights reserved. The contents of this document are confidential and proprietary to IQVIA Holdings Inc. and its subsidiaries. Unauthorized use, disclosure or reproduction is strictly prohibited.

Term	Definition
	that reclassifies their disease from moderate severity to mild severity
Therapeutic failure	Participant who are non-responder at week 24. This participant will discontinue study treatment
Enrolled	The participant agrees to participate in the clinical study by completing the informed consent process.

Copyright © 2009, 2010, 2012, 2016, 2018, 2019, 2021, 2024 IQVIA. All rights reserved. The contents of this document are confidential and proprietary to IQVIA Holdings Inc. and its subsidiaries. Unauthorized use, disclosure or reproduction is strictly prohibited.

